4.6.2.4 Electrocardiograms

ECG variables will be summarized using mean, standard deviation, minimum, maximum and median for each treatment group and overall at each treatment visit and time point, including changes from baseline.

Number and percent of participants with normal, not clinically significant abnormal, and clinically significant abnormal results as assessed by investigator for the 12 lead ECG will be tabulated by treatment group and overall at each treatment visit and time point.

The heart rate, PR, and QTc interval will be summarized using frequency tables for each treatment visit and time point for values of clinical importance using the range criteria below.

Table 7 Potentially Clinically Significant Criteria for ECG

ECG Parameter	Age Group	Pre-specified Level
PR	6 – 11 months	<70, >159
	12 – 23 months	<71 msec, >160 msec
	2 – 3 years	<75 msec, >165 msec
	4 – 5 years	<80 msec, >166 msec
	6 – 7 years	<83 msec, >170 msec
	> 7 years	<85 msec, >182 msec
QTc (Fridericia's)	Any	>450 msec, > 480 msec, >500 msec
QRS	6 – 11 months	< 40, > 101 milliseconds
	12 – 23 months	< 40, > 105 msec
	2 – 3 years	< 40, > 115 msec
	4 – 5 years	< 41, > 125 msec
	6 – 7 years	< 52, > 118 msec
	> 7 years	< 60, > 122 msec
Heart rate	6 – 11 months	< 65, 188 beats/min
	12 – 23 months	< 56, > 184 beats/min
	2 – 3 years	< 46, > 168 beats/min
	4 – 5 years	< 38, > 146 beats/min
	6 – 7 years	< 40, > 128 beats/min
	> 7 years	< 30, > 122 beats/min

The QTc interval will also be summarized by the frequencies of participants with a change from baseline of clinical importance using the criteria identified below. These summaries will be provided for each treatment visit and time point.

Table 8 Potentially Clinically Significant Criteria for QTc

Variable	Change from Baseline
QTc Interval (msec)	> 30
	> 60

Number and percent of participants whose 12 lead ECG reading changed from normal at baseline to abnormal will be tabulated by treatment group at each treatment visit and time point.

Listings will present ECG data, such as overall interpretation of ECGs, assessments of heart rate (HR), and intervals of PR, QRS, QT, QTc (with method), as well as other specifications. The listing will flag any results that are outside the levels provided in the table above.

4.6.2.5 Other Safety-Related Assessments

4.6.2.5.1 Echocardiogram

Number and percentage of participants with abnormal ECHO findings will be summarized by time point (and clinical significance if feasible). Participant listings of ECHO findings and descriptions will be provided.

4.6.2.5.2 Liver Ultrasound

Number and percentage of participants with abnormal liver ultrasound findings will be summarized by time point and clinical significance if feasible. Participant listing of liver ultrasound findings and descriptions will be provided.

4.6.2.5.3 Hospitalization

The annualized hospitalization rate will be summarized by dose level group and overall. The participant-year-adjusted rate is calculated for each participant by:

$$\frac{\text{Sum of the number of hospital admissions recorded on the AE eCRF}}{(\text{max}(\text{Date of last day of follow up, date of discontinuation}) - \text{date of dosing} + 1) / 365.25}$$

Summary statistics of this rate will be tabulated. In addition, the annualized hospitalization rate will be summarized by counts and percentages in the following categories:

- 0 hospitalizations
- < 1 hospitalization/patient-year
- 1-2 hospitalization/patient-year
- 2-3 hospitalizations/patient-year
- 3-4 hospitalizations/patient-year
- 4-5 hospitalizations/patient-year
- >= 5 hospitalizations/patient-year

Length of stay per hospitalization will be summarized descriptively as a continuous variable. Length of stay is calculated as the discharge date – admission date + 1. If a participant has multiple hospital stays with multiple corresponding durations, then all will be included in the summary statistics.

Participants' hospitalization information will also be listed.

4.6.2.6 Growth Parameters and Physical Examination

Growth parameters will be summarized descriptively.

Growth parameters and physical examinations will be listed.

4.7 Other Analyses

4.7.1 Other Variable and/or Parameters

4.7.1.1 Analysis of Immunogenicity

All available antibody titer (anti-AAV8 (NAB), anti-AAV8 (TAB), anti-MTM1) data will be included in a participant listing. Antibody titers that are below the limit of detection (BLD) values will be presented as “BLD” in the listing and footnoted accordingly.

Summaries will be created for tabulating the incidence (and percent) of immune response by treatment group and assay type.

Spider plots of titer levels will be created by dose level group for each assay type.

4.7.1.2 Biodistribution and Vector Shedding

All available vector DNA in muscle biopsy data and vector shedding data will be included in a participant listing.

Vector DNA in muscle biopsies will be summarized descriptively by visit and dose level group.

Maximum vector DNA concentrations (Cmax) and time to achieve maximum concentration in shedding matrices (Tmax) will be summarized descriptively by dose level group.

The duration of vector shedding will be summarized descriptively by dose level using Kaplan-Meier plots along with median (95% CI) and quartile time from the administration of study drug to event. Additional summary statistics will be provided for participants who are not censored.

The event of 'end of vector shedding' is defined as the date of the first of three vector shedding results measured as below the lower limit of quantification (LLOQ). Participants will be censored at the last known date/time of contact.

Spider plots of vector shedding data over time will be created by dose level group.

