5.1.1.27 Viral Shedding

Viral shedding will be assessed by quantitative polymerase chain reaction (PCR) on samples of saliva (swab), stool sample, and urine (diaper collection or urine bag). Collection of each sample type will begin on Day 1 and will continue until each sample type has 3 consecutive data points at or below the limit of detection (BLOD). For example, saliva collection will stop once 3 consecutive saliva sample results are BLOD, but stool and urine collection will continue beyond that timepoint if they have not reached 3 consecutive BLOD results in each of those individual sample types. Sponsor will notify the site when collection can cease.

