Control participants will generally have the same assessments as treated participants but on a less frequent schedule to lessen the burden of study participation. It is anticipated that control participants will participate for at least 24 weeks before an optimal dose is determined and the participant can be administered AT132. Following determination of the optimal dose, control participants will undergo pretreatment baseline procedures to confirm that they remain eligible to receive treatment with AT132 at the optimal dose. Once eligible, control participants will be dosed with AT132, and will initiate the post dose procedures.

Treated participants will be administered a course of concomitant prophylactic glucocorticoid (oral prednisolone) therapy commencing 1 day prior to AT132 dosing, and continuing for a period of approximately 8 weeks, then tapering from the original dose over an additional 8 weeks, per Investigator discretion, as a preventative measure for immune-mediated hepatic injury, which has been observed in gene therapy clinical studies with AAV. Tapering duration may be altered and/or supplemental administration of IV steroids (e.g., methylprednisolone) or other immunosuppressive regimens may be considered in cases of potential malabsorption of oral medications.

Participants will be followed for a total of 10 years following AT132 administration. See Figure 1 for the individual study participation timeline (Parts 1 & 2) through Week 48.

Part 2 (described herein as planned prior to protocol v8; partially dosed as of protocol v8):

In Part 2, the optimal dose of AT132 will be evaluated in an expansion cohort of 10 participants age matched randomized to a study drug or a delayed-treatment control group

(1:1 allocation ratio). A pair of participants in each group will be prospectively best-matched based on age (± 6 months) before being randomized to 1 of the treatment arms (AT132 vs. delayed-treatment control). The administration of study drug and concomitant prophylactic glucocorticoids, and the assessment of safety will be the same as described in Part 1. Following collection of their Week 24 data, control participants will be administered AT132 and followed according to the Schedule of Events.

Part 2 as of protocol v8 and v9:

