4.4.2.2.8 Survival

This endpoint will be summarized for low dose and the high dose groups separately for all participants in the FAS. Kaplan-Meier plots of time from the dosing date to event will be provided. In addition, the estimated survival rate at the following time-points will be presented by dose level group:

- 3 months
- 6 months
- 1 year
- 2 years
- 5 years
- 10 years

For this analysis, the date of a participant's death is considered the time of an event. Survival status should be assessed at each visit until the participant withdraws consent or completes the study. If the participant misses a visit or withdraws for a reason other than withdrawal of consent or death, the site should contact the parent(s)/LAR(s) to ascertain if the participant is

alive. For participants who withdraw from the study, the participant should be contacted every 6 months for 5 years after administration and every year for an additional 5 years (after the 5-year follow-up through 10-years follow-up) to assess for survival. If not alive, the cause and date of death should be requested and recorded.

Participants will be censored at the last known date/time of contact.

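### The SAP's end-of-shedding rule requires neither consecutive results nor a single sample type, and it censors at last contact, so Kaplan-Meier shedding durations can be misstated

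*SAP*

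**What the plan says.** SAP 4.7.1.2 (Biodistribution and Vector Shedding) gives the method: "The duration of vector shedding will be summarized descriptively by dose level using Kaplan-Meier plots along with median (95% CI") and quartiles, measured from dosing. The event, end of shedding, is "the date of the first of three vector shedding results measured as below the lower limit of quantification (LLOQ"). For everyone else, "Participants will be censored at the last known date/time of contact". The section names no sample type for this analysis and does not say whether the three results must follow one another.

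Protocol 5.1.1.27 collects "samples of saliva (swab), stool sample, and urine (diaper collection or urine bag") from Day 1, and collection "will continue until each sample type has 3 consecutive data points at or below the limit of detection (BLOD"). The worked example there shows that the rule runs separately by sample type: "saliva collection will stop once 3 consecutive saliva sample results are BLOD", while stool and urine carry on. The footnotes on viral shedding in the schedules of events (Protocol 5.4 and 5.5) repeat the rule.

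Scheduled shedding samples run to Month 60 (Protocol 5.5); the schedule from Month 72 to Month 120 (Protocol 5.6) has no shedding row. Contact lasts longer. "Participants will be followed for a total of 10 years following AT132 administration" (SAP 1.2), and survival contact goes on after withdrawal: "For participants who withdraw from the study, the participant should be contacted every 6 months for 5 years after administration" (SAP 4.4.2.2.8), then yearly.

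**The concern.** Three elements of the collection rule are absent from the SAP event: consecutive results, the detection limit, and separation by sample type.

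- **Consecutive.** If the three low results may be scattered, one isolated low value can date the end of shedding even though later samples are positive.
- **Sample type.** If types may be mixed, the saliva, stool and urine samples of a single visit could supply all three results.
- **Threshold.** A child with vector detected but below LLOQ counts as finished in the analysis while the protocol still calls for samples.

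The censoring rule is a separate problem. A child whose sampling stopped early without the event stays in the risk set through time in which no event could have been recorded.

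Viral shedding is a listed safety endpoint, and its duration is one of the SAP's summaries of it. The SAP version history gives data needed for the label as the reason for revising this section. The dose groups are small, so a few misdated children can move a median or quartile.

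**Working it through.** The plan states no shedding duration, LOD or LLOQ, so there is no figure to reproduce. The check applies both rules to hypothetical results on the protocol's sampling days: 1, 2, 3, 7, 21, 35, 49, 63, 77, 91, 105, 168, 252, 336, 548, then each six-monthly visit to 1825 (Protocol 5.4 and 5.5).

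**Event date, one sample type.** Q = quantifiable, L = detected but below LLOQ, N = at or below LOD. All sequences are invented.

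| Pattern from Day 1 | Any three < LLOQ | Three consecutive < LLOQ | Three consecutive ≤ LOD |
|---|---|---|---|
| Intermittent: QQQQQQLQQNQNNN… | Day 49 | Day 168 | Day 168 |
| Long low tail: QQQQQQLLLLLNNN… | Day 49 | Day 49 | Day 168 |
| Clean clearance: QQQQQQQNNN… | Day 63 | Day 63 | Day 63 |

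In the first row the low results fall on Days 49, 91 and 168, with quantifiable results on Days 63, 77 and 105. The literal rule therefore ends shedding on Day 49, before three positive samples. The second row isolates the threshold: adding the word consecutive changes nothing there. In the third row the rules agree.

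Direction: if LOD lies below LLOQ, three consecutive results at or below LOD are also three results below LLOQ. The literal SAP date can then be equal or earlier, never later.

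**Simulation under stated assumptions.** The log10 level starts at a normal mean of 5 (SD 0.7) and falls by one log10 every 2h days, with h log-normal (median 12, log SD 0.4). LOD is 1, LLOQ is 0 to 1.0 log10 above it, noise SD is 0 to 1.0, with 4,000 participants per setting. The median was Day 63 to 105 under the literal SAP rule and Day 105 under three consecutive results ≤ LOD. The SAP date was earlier in 0% to 87% of participants. Requiring consecutive results alone moved the median by 0 to 28 days; the rest came from the threshold. Other decline rates would give other gaps, so this shows a mechanism and does not estimate its size in this trial.

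**Censoring.** Take ten hypothetical children: events on Days 63, 77, 91, 105, 105, 168, 168 and 252, and two without the event whose last samples were on Days 49 and 77.

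- Censored at last sample: S(105) = (8/9) × (7/8) × (5/6) × (3/5) = 0.39.
- Censored at last contact, years later: S(105) = (9/10) × (8/9) × (7/8) × (5/7) = 0.50.

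The first day with S at or below 0.5 is Day 105 in both, although the second estimate sits exactly on 0.50. If the two children had instead been sampled to Month 60, moving their censoring date from Day 1825 to Day 3650 changes nothing, because no scheduled sample can record an event after Day 1825.

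**The case against.** The best defence is that the SAP says the first of three and never says any three. The SAP presents itself as an elaboration of the protocol's analysis, and the protocol's only three-result rule is consecutive, so consecutive may well be what was meant. That is fair, but the text is silent and a programmer following it literally could produce the earlier date.

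A reader might infer that the SAP breaches a protocol requirement. The documents do not support that. The protocol rule says when collection stops; for analysis, Protocol 7.4.1.2 says only that viral shedding will be summarized, and Protocol Section 7 makes the final SAP the analysis of record. A collection threshold and an analysis threshold may legitimately differ, so LOD is not the only defensible choice.

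The censoring effect is also narrow. With LOD below LLOQ, a child whose collection stopped under the protocol rule already has the SAP event and is not censored. A child without the event should still be sampled to Month 60. Only withdrawal or missed sampling, while other children are still having events, changes the curve.

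Finally, the SAP lists all shedding data and produces spider plots over time, so a rebound after an early low value would be visible, and no hypothesis is tested. These displays would expose a wrong date but would not correct the Kaplan-Meier median.

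**Conclusion.** The point stands as an ambiguous event rule and an unsuitable censoring rule, either of which can give a wrong Kaplan-Meier estimate. The literal event rule can understate duration; last-contact censoring can overstate the proportion still shedding. They act on different children, so they cannot be assumed to cancel. The net direction is unknown.

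Three stronger readings go too far. That durations will be misstated: clean clearance gives identical dates, and consecutive results may have been intended. That the error can be given in days: the documents contain no assay limits, decline rate or results, and the figures above rest on assumptions. That shedding duration is itself a listed safety endpoint: Protocol Section 2 and SAP 1.1.2 list viral shedding, and duration appears only as a summary in SAP 4.7.1.2.

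The direction of the event-date effect assumes that LOD lies below LLOQ. No alpha, power or sample size is affected. The change should be made before database lock.

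**What to change.** Reword SAP 4.7.1.2:

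- Analyse saliva, stool and urine separately.
- Define the end of shedding as the date of the first of three consecutive post-dose results that meet one stated threshold. Use at or below the limit of detection, to match the collection rule, or below LLOQ with the reason given.
- Censor children without the event at the last evaluable shedding sample of that type.

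The cost is SAP text and programming. No new data are needed, because sample-level results are already to be listed. Estimates could move either way: the event change can only leave a date unchanged or make it later, while the censoring change can lower the estimated proportion still shedding.

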4.7.2 Subgroup Analyses

Subgroup analyses are not planned for this study.

4.8 Interim Analysis (and Early Discontinuation of the Clinical Study)

There will be no formal interim analysis.

4.9 Sample Size Determination

The following language was from protocol v9 that planned a formal analysis to compare 1.3×10^{14} vg/kg and delayed-treatment control, however given that the study will not be able to address the objectives, no such formal analysis will be conducted.

A power analysis for the primary analysis of the primary endpoint was conducted at 80% power and 0.05 level of alpha to estimate the required sample size based on Mean of 13.0 vs. 0.0 hours of reduction in ventilation need, with common SD of 6.0 by Week 24 using a t-test, resulting in at least $N = 10$ for a balanced 1:1 allocation between 1.0×10^{14} vg/kg AT132 (equates to 1.3×10^{14} vg/kg as determined by the 2nd generation vg titer assay) and delayed-treatment control. It is further assumed, that the same difference in means (SD), will provide at least 80% power using a MMRM analysis proposed for the primary endpoint. However, it is possible that 1:1 allocation may not be feasible; 1 control participant serving as control for multiple treated participants, or multiple control participants being a match for a single treated participant. Therefore, all qualified control participants will be used in the analyses to

ensure adequate power is available to detect the intended difference between treated and control participants.

4.10 Additional Conventions

4.10.1 Baseline Definition

Unless otherwise specified, baseline is defined as the last assessment collected in ASPIRO study prior to time/date of dosing with study drug.

4.10.2 Analysis Windows

The data summary by visits will be done following the analysis windows specified in the [tables](#) below:

Table 9 Analysis Visit Windows for Efficacy Endpoints

Analysis Visits	Scheduled Day in Protocol (Day)	Analysis Windows (Day)								
		(a) Ventilator param., MIP, MEP, P0.1, tidal volume, ventilator weaning & discont.	(b) Secretion manage. assessment (PGIS-S, PGIS-I)	(c) Motor develop. milestone,	(d) Bayley-III, motor domain	(e) CHOP INTEND, MFM-32	(f) ACEND	(g) PedsQL	(h) Clinical global impression scales, Swallowing questionnaire, Communicative development inventories	(i) Ventilator Depend. Question.
Baseline	-1	≤ -1	≤ -1	≤ -1	≤ -1	≤ -1	≤ -1	≤ -1	≤ -1	≤ -1
Dosing	1									
Day 2	2									
Day 3	3									
Week 1	7						1-10	1-10	1-10	1-17
Week 2	14	1-21				1-21	11-21	11-21	11-21	
Week 3	21									
Week 4	28	22-56	1-42	1-56	1-56	22-42	22-56	22-56	22-42	18-56
Week 5	35									
Week 6	42									
Week 7	49									
Week 8	56		43-70			43-70			43-70	
Week 9	63									
Week 10	70									
Week 11	77									
Week 12	84	57-98	71-98	57-98	57-98	71-98	57-98	57-98	71-98	57-98
Week 13	91									
Week 14	98									
Week 15	105									
Week 16	112	99-140	99-126	99-140	99-140	99-140	99-140	99-140	99-140	99-140
Week 20	140		127-154							
Week 24	168	141-252	155-182	141-210	141-210	141-210	141-210	141-210	141-210	141-182
Week 28	196		183-210							183-210
Week 32	224		211-238							211-238
Week 36	252		239-266	211-294	211-294	211-294	211-294	211-294	211-294	239-266
Week 40	280		267-294							267-294
Week 44	308		295-322							295-322
Week 48	336	253-442	323-442	295-396	295-396	295-442	295-442	295-442	295-442	323-396
Month 15	456			397-502	397-502					397-502
Month 18	548	443-639	443-639	503-639	503-639	443-639	443-639	443-639	443-639	503-639

Analysis Visits	Scheduled Day in Protocol (Day)	Analysis Windows (Day)								
		(a) Ventilator param., MIP, MEP, P0.1, tidal volume, ventilator weaning & discount.	(b) Secretion manage. assessment (PGIS-S, PGIS-I)	(c) Motor develop. milestone,	(d) Bayley-III, motor domain	(e) CHOP INTEND, MFM-32	(f) ACEND	(g) PedsQL	(h) Clinical global impression scales, Swallowing questionnaire, Communicative development inventories	(i) Ventilator Depend. Question.
Month 24	730	640-821	640-821	640-821	640-821	640-821	640-821	640-821	640-821	640-821
Month 30	[contact]	822-1004	822-1004	822-1004	822-1004	822-1004	822-1004	822-1004	822-1004
Month 36	1095	1005-1186	1005-1186	1005-1186	1005-1186	1005-1186	1005-1186	1005-1186	1005-1186	1005-1186
Month 42	1278	1187-1369	1187-1369	1187-1369	1187-1369	1187-1369	1187-1369	1187-1369	1187-1369	1187-1369
Month 48	1460	1370-1551	1370-1551	1370-1551	1370-1551	1370-1551	1370-1551	1370-1551	1370-1551	1370-1551
Month 54	1643	1552-1734	1552-1734	1552-1734	1552-1734	1552-1734	1552-1734	1552-1734	1552-1734	1552-1734
Month 60	1825	≥1735	≥1735	1735-2007	≥1735	≥1735	1735-2007	≥1735	≥1735	1735-2007
Month 72	2190			2008-2372			2008-2372			2008-2372
Month 84	2555			2373-2737			2373-2737			2373-2737
Month 96	2920			2738-3102			2738-3102			2738-3102
Month 108	3285			3103-3467			3103-3467			3103-3467
Month 120	3650			≥3468			≥3468			≥3468

Abbreviations: NA = Not Applicable.
 Grey area indicates NA.

Table 10 Analysis Visit Windows for Safety Endpoints

Analysis Visits	Scheduled Day in Protocol (Day)	Analysis Windows (Day)												
		(a) LFTs, CK (including CK isoenzymes), CRP, serum bicarbonate (local & central)	(b) Chemistry excluding (a), hematology (local & central)	(c) Urinalysis (local & central)	(d) Cytokine panel, complement panel (central)	(e) Troponin T and/or I (local & central)	(f) Coagulation (local)	(g) Viral Shedding (central)	(h) Serum bile acid (central)	(i) Platelet monitoring	(i) Vital signs	(j) 12-Lead ECG	(k) Liver ultrasound	(l) Anti-AAV8, Anti-MTM1 (central)
Baseline	-1	≤ -1	≤ -1	≤ -1	≤ -1 [#]	≤ -1	≤ -1		≤ -1	≤ -1	≤ 1*	≤ -1	≤ -1	
Dosing	1							1			1*			
Day 2	2	1-4	1-4	1-4		1-4		2		1-4	2	1-4		
Day 3	3				1-5			3-5			3-5			
Wk 1	7	5-10	5-10	5-10	6-10	5-10	1-17	6-14		5-10	6-10	5-10		
Wk 2	14	11-17	11-21	11-21	11-17	11-17				≥11	11-21	11-21		
Wk 3	21	18-24			18-24	18-24		15-28						
Wk 4	28	25-31	22-42	22-42	25-31	25-35	18-42				22-42	22-42	1-56	1-35
Wk 5	35	32-38			32-38			29-42						
Wk 6	42	39-45			39-45	36-49								36-49
Wk 7	49	46-52			46-52			43-56						
Wk 8	56	53-59	43-70	43-59	53-59	50-59	43-112				43-70	43-70		50-70
Wk 9	63	60-66		60-66	60-66	60-66		57-70						
Wk 10	70	67-73		67-73	67-73	67-73								
Wk 11	77	74-80		74-80	74-80	74-80		71-84						
Wk 12	84	81-87	71-98	81-98	81-87	81-87			1-126		71-98	71-98	57-98	71-98
Wk 13	91	88-94			88-94	88-94		85-98						
Wk 14	98	95-101			95-101	95-101								
Wk 15	105	102-108			102-108	102-108		99-136						
Wk 16	112	109-140	99-140	99-140	109-140	109-140					99-140	99-140	99-140	99-140
Wk 24	168	141-210	141-210	141-210	141-210	141-210	113-210	137-210	127-210		141-210	141-210	141-210	141-210
Wk 36	252	211-294	211-294	211-294	211-294	211-294	211-294	211-294	211-294		211-294	211-294	211-294	211-294
Wk 48	336	295-442	295-442	295-442	295-442	295-442	295-442	295-442	295-396		295-396	295-442	295-442	295-442
Mth 15	456								397-502		397-502			
Mth 18	548	443-639	443-639	443-639	443-639	443-639	443-639	443-639	503-639		503-639	443-639	443-639	443-639
Mth 24	730	640-821	640-821	640-821	640-821	640-821	640-821	640-821	640-821		640-821	640-821	640-821	640-821
Mth 30	[contact]	822-1004	822-1004	822-1004	822-1004	822-1004	822-1004	822-1004		822-1004	822-1004	822-1004	822-1004
Mth 36	1095	1005-1186	1005-1186	1005-1186	1005-1186	1005-1186	1005-1186	1005-1186	1005-1186		1005-1186	1005-1186	1005-1186	1005-1186

Footnotes

Analysis Visits	Scheduled Day in Protocol (Day)	Analysis Windows (Day)												
		(a) LFTs, CK (including CK isoenzymes), CRP, serum bicarbonate (local & central)	(b) Chemistry excluding (a), hematology (local & central)	(c) Urinalysis (local & central)	(d) Cytokine panel, complement panel (central)	(e) Troponin T and/or I (local & central)	(f) Coagulation (local)	(g) Viral Shedding (central)	(h) Serum bile acid (central)	(i) Platelet monitoring	(i) Vital signs	(j) 12-Lead ECG	(k) Liver ultrasound	(l) Anti-AAV8, Anti-MTM1 (central)
Mth 42	1278	1187-1369	1187-1369	1187-1369	1187-1369	1187-1369	1187-1369	1187-1369	1187-1369		1187-1369	1187-1369	1187-1369	1187-1369
Mth 48	1460	1370-1551	1370-1551	1370-1551	1370-1551	1370-1551	1370-1551	1370-1551	1370-1551		1370-1551	1370-1551	1370-1551	1370-1551
Mth 54	1643	1552-1734	1552-1734	1552-1734	1552-1734	1552-1734	1552-1734	1552-1734	1552-1734		1552-1734	1552-1734	1552-1734	1552-1734
Mth 60	1825	≥1735	1735-2007	≥1735	≥1735	≥1735	≥1735	≥1735	≥1735		≥1735	≥1735	1735-2007@	≥1735
Mth 72	2190		2008-2372						2008-2372@				2008-2372	
Mth 84	2555		2373-2737						2373-2737@				2373-2737	
Mth 96	2920		2738-3102						2738-3102@				2738-3102	
Mth 108	3285		3103-3467						3103-3467@				3103-3467	
Mth 120	3650		≥346						≥3468@				≥3468	

Abbreviations: CRP = C-creative protein; Local = Local Lab; Central = Central Lab; NA = Not Applicable; Wk = Week; Mth = Month.

Grey area indicates NA.

#Only Applicable to Cytokine panel.

*As per the study protocol and SAP: For Vital Signs assessment on Dosing Day 1, if the assessment time was prior to Dosing time, then the assessment will be used as Baseline; if the assessment time is after Dosing time, then the assessment will be under "Day 1" visit.

@Only Applicable to Serum Bile Acid, Total.

Table 11 Analysis Week Window for Weekly Average Hours of Ventilator Support from Diary of Ventilator Dependence

Analysis Week	Analysis Windows (Day)
Baseline	-7 - -1
Week 1	1 - 7
Week 2	8 - 14
Week 3	15 - 21
Week 4	22 - 28
Week 5	29 - 35
Week 6	36 - 42
Week 7	43 - 49
Week 8	50 - 56
Week 9	57 - 63
Week 10	64 - 70
Week 11	71 - 77
Week 12	78 - 84
Week 13	85 - 91
Week 14	92 - 98
Week 15	99 - 105
Week 16	106 - 112
Week 17	113 - 119
Week 18	120 - 126
Week 19	127 - 133
Week 20	134 - 140
Week 21	141 - 147
Week 22	148 - 154
Week 23	155 - 161
Week 24	162 - 168
Week 25	169 - 175
Week 26	176 - 182
Week 27	183 - 189
Week 28	190 - 196
Week 29	197 - 203
Week 30	204 - 210
Week 31	211 - 217
Week 32	218 - 224
Week 33	225 - 231
Week 34	232 - 238
Week 35	239 - 245
Week 36	246 - 252
Week 37	253 - 259
Week 38	260 - 266
Week 39	267 - 273
Week 40	274 - 280
Week 41	281 - 287
Week 42	288 - 294
Week 43	295 - 301
Week 44	302 - 308
Week 45	309 - 315
Week 46	316 - 322
Week 47	323 - 329
Week 48	330 - 336

If more than one observation exists within the analysis window, the observation closest to the scheduled visit day will be selected for that visit. If there are two observations that have the same distance from the scheduled day, the value that is after the scheduled day will be

selected in the analysis. If more than one observation is made on the same day, an average value if continuous or the worst value if categorical will be included in the analysis.

The Follow Up visit will include all data collected beyond 10 days after the last dose of study drug. If there is more than one value, then the value that is closest to day 28 from the last dose of study drug will be selected for the analysis. The same logic will be applied as above for more than one value.

If a table summary for visits is not planned, then visit windowing does not need to be done for that data.

For diary data, results will be mapped to a particular visit week by the following logic, which is the same as in [Table 11](#):

```
avisit="Week "||strip(put(ceil(ady/7),best.))
```

Per protocol, daily diary collection should end after Week 48. However, for some participants it continued longer. For daily diary analysis visits that correspond to a “Month X” official analysis visit name, the avisit calculation above will be converted to the corresponding Month X official analysis according to the analysis windows table.

